In addition, while in the ICU all study subjects will be monitored with a non-invasive respiratory monitor (Expiron) to determine respiratory rate, tidal volume, minute volume and breathing pattern for up to 96 hours. This monitoring will aid in

detection of respiratory depression and add additional safety to the trial. This device measures chest expansion by thoracic impedance and is FDA approved.

Supplemental oxygen will be provided to maintain a peripheral oxygen saturation of 90% or greater.

Injections will be performed by trained trauma / critical care physicians. Training prior to initiating the study will include familiarization with the standardized procedure as described below, which will be documented in study records. Patients will be monitored by bedside nurses before, during, and after the block procedure. Standard inpatient cardiac arrest carts will be immediately available before, during, and after the block procedure.

A 20-mL vial will be obtained from IDS Pharmacy that either contains liposomal bupivacaine (266 mg in 20-mL) or 0.9% sodium chloride. Patients will be positioned either sitting up or in logroll/decubitus position. Rib fractures will be noted from previously obtained CT scan of the chest from initial trauma evaluation. The thoracic posterolateral area will be prepped and draped in sterile fashion. After aspiration to prevent intravascular injection, 1 mL of liposomal bupivacaine will be injected with a 25-G needle just below each affected rib by the intercostal neurovascular bundle in a posterior but not paravertebral position or 0.9% saline (as placebo control) will be injected with a 25-G needle in the subcutaneous space just superficial to each affected rib to minimize risk of placebo-injection complications. Optimal regional blockade will include the rib immediately above the most superior and the rib immediately below the most inferior fractured rib.

Regional blockade will only be performed once per patient enrolled in the study and at one injection site per fractured rib. Patients will only be enrolled once per acute traumatic event and admission.

If a patient enrolled in the study should have an adverse event during the course of intercostal rib block administration and the reaction is severe or life-threatening, then the patient will be withdrawn from the study and no further injections will be administered, regardless of how many injections were originally planned.

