There may be temporary pain or local discomfort associated with repeated intercostal injections. Additionally, there will be a small risk of a pneumothorax if the intercostal injection needle violates the parietal pleura.

Additionally, the trauma team will have discretion to hold or stop enoxaparin doses if patient is deemed to have bleeding. Patients may also have doses held due to perioperative plans. This will also allow for appropriate, safe patient care.

If a patient enrolled in the study should have an adverse event during the course of the intercostal rib block administration and the reaction is severe or life threatening, then the patient will be withdrawn from the study and no further injections will be administered, regardless of how many injections were originally planned. In addition, an adverse event based on physiologic response will include a sustained (greater than five minute) change in heart rate by > 40% from baseline or absolute heart rate greater than 160 or less than 50, change in systolic blood pressure by 40% or absolute systolic blood pressure less than 80 mmHg or greater than 180 mmHg, change in respiratory rate by 50% or absolute respiratory rate greater than 30 or less than 6, or decreasing oxygen saturation

by 10% SpO₂ or less than absolute SpO₂ < 85%. Any non-sinus rhythm or ST segment changes seen on the EKG monitoring strip will lead to immediate subject discontinuation.

Safety Assessments

Every adverse event, whether or not thought to be related to study drug, will be recorded and entered into the RAVE Case Report Form database.

Any medical condition present prior to study enrollment should not be reported as an adverse event, unless the medical condition worsens in severity or seriousness during the study. In this case it may be reported as an adverse event at the discretion of the Investigator.

The Investigator will review each event and assess its severity and relationship to the study treatment.

Adverse event Definitions:

Adverse Event

Adverse event means any untoward medical occurrence associated with the use of a drug in humans, whether or not considered drug related.

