An adverse event or suspected adverse reaction is considered “life-threatening” if, in the view of either the investigator or sponsor, its occurrence places the patient or subject at immediate risk of death. It does not include an adverse event or suspected adverse reaction that, had it occurred in a more severe form, might have caused death.

Table 9.3. Causality Definitions:

Causality term	Assessment criteria*
Certain	
• Event or laboratory test abnormality, with plausible time relationship to drug intake• Cannot be explained by disease or other drugs• Response to withdrawal plausible (pharmacologically, pathologically)• Event definitive pharmacologically or phenomenologically (i.e. an objective and specific medical disorder or a recognised pharmacological phenomenon)• Rechallenge satisfactory, if necessary

Probable/ Likely	
 Event or laboratory test abnormality, with reasonable time relationship to drug intake Unlikely to be attributed to disease or other drugs Response to withdrawal clinically reasonable Rechallenge not required
Possible	
 Event or laboratory test abnormality, with reasonable time relationship to drug intake Could also be explained by disease or other drugs Information on drug withdrawal may be lacking or unclear
Unlikely	
 Event or laboratory test abnormality, with a time to drug intake that makes a relationship improbable (but not impossible) Disease or other drugs provide plausible explanations
Conditional/ Unclassified	
 Event or laboratory test abnormality More data for proper assessment needed, or Additional data under examination
Unassessable/ Unclassifiable	
 Report suggesting an adverse reaction Cannot be judged because information is insufficient or contradictory Data cannot be supplemented or verified

Table 9.4. Toxicity Grading Scale:

Local Reaction to Injectable	Mild (Grade 1)	Moderate(Grade 2)	Severe (Grade 3)	Potentially Life Threatening (Grade 4)
Pain	Does not interfere with activity	Repeated use of non-narcotic pain reliever > 24 hours or interferes with activity	Any use of narcotic pain reliever or prevents daily activity	Emergency room (ER) visit or hospitalization
Tenderness	Mild discomfort to touch	Discomfort with movement	Significant discomfort at rest	ER visit or hospitalization

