Erythema/Redness*	2.5 – 5 cm	5.1 – 10 cm	> 10 cm	Necrosis or exfoliative dermatitis
Induration/Swelling**	2.5 – 5 cm and does not interfere with	5.1 – 10 cm or interferes with activity	> 10 cm or prevents daily activity	Necrosis

*In addition to grading the measured local reaction at the greatest single diameter, the measurement should be recorded as a continuous variable.

**Induration/Swelling should be evaluated and graded using the functional scale as well as the actual measurement.

Vital Signs *	Mild (Grade 1)	Moderate(Grade 2)	Severe (Grade 3)	Potentially Life Threatening (Grade 4)
Fever (°C) ** (°F) **	38.0 – 38.4 100.4 – 101.1	38.5 – 38.9 101.2 – 102.0	39.0 – 40 102.1 – 104	> 40 > 104
Tachycardia - beats per minute	101 – 115	116 – 130	> 130	ER visit or hospitalization for arrhythmia
Bradycardia - beats per minute***	50 – 54	45 – 49	< 45	ER visit or hospitalization for arrhythmia
Hypertension (systolic) - mm Hg	141 – 150	151 – 155	> 155	ER visit or hospitalization for malignant hypertension
Hypertension (diastolic) - mm Hg	91 – 95	96 – 100	> 100	ER visit or hospitalization for malignant hypertension
Hypotension (systolic) – mm Hg	85 – 89	80 – 84	< 80	ER visit or hospitalization for hypotensive shock
Respiratory Rate – breaths	17 – 20	21 – 25	> 25	Intubation

* Subject should be at rest for all vital sign measurements.

** Oral temperature; no recent hot or cold beverages or smoking.

*** When resting heart rate is between 60 - 100 beats per minute. Use clinical judgment when characterizing bradycardia among some healthy subject populations, for example, conditioned athletes.

Systemic (General)	Mild (Grade 1)	Moderate(Grade 2)	Severe (Grade 3)	Potentially Life Threatening (Grade 4)
Nausea/vomiting	No interference with activity or 1 – 2 episodes/24 hours	Some interference with activity or > 2 episodes/24 hours	Prevents daily activity, requires outpatient IV hydration	ER visit or hospitalization for hypotensive shock
Diarrhea	2 – 3 loose stools or < 400 gms/24 hours	4 – 5 stools or 400 – 800 gms/24 hours	6 or more watery stools or > 800gms/24 hours or requires outpatient IV hydration	ER visit or hospitalization
Headache	No interference with activity	Repeated use of non-narcotic pain reliever > 24 hours or some	Significant; any use of narcotic pain reliever or prevents daily activity	ER visit or hospitalization
Fatigue	No interference with activity	Some interference with activity	Significant; prevents daily activity	ER visit or hospitalization

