Myalgia	No interference with activity	Some interference with activity	Significant; prevents daily activity	ER visit or hospitalization

Table 9.4 extracted from: Guidance for Industry, Toxicity Grading Scale for Healthy Adult and Adolescent Volunteers Enrolled in Preventive Vaccine Trials, U.S. Department of Health and Human Services, Food and Drug Administration, Center for Biologics Evaluation and Research, August 2016

Treatment of cardiovascular and neurologic adverse events

- Local anesthetic systemic toxicity
 - Treatment will be initiated as recommended as the American Society of Regional Anesthesia and Pain Medicine, according to the society's checklist (Appendix)
- Treatment will include: transfer to intensive care unit setting if not already in intensive care unit, continuous hemodynamic monitoring for at least 24 hours, appropriate airway management with assistance from respiratory therapy and a critical care consultant as needed, cardiovascular stabilization and assistance from a critical care consultant as needed, administration of Lipid Emulsion therapy, as per ASRA checklist in Appendix, Neurology consult for any observed systemic neurologic toxicity (including change in vision, mental status change, persistent headache, seizure), Cardiology consult for any arrhythmias that persist greater than 30 minutes, beyond initial appropriate medical treatment, or result in hypotension with systolic blood pressure < 80mmHg.

10. Data Safety monitoring plan and/or DSMB:

Patients will be screened for the adverse events described above.

Adverse events will be continuously assessed on an ongoing basis by [name], medical monitor. Study will be stopped if:

- **Adverse events probably/likely or certainly related to study drug, regardless of severity, occur in > 10% of enrolled patients, or**
- **Serious/life-threatening adverse events, regardless of causality, occur in > 2% of enrolled patients.**

11. Data Analysis:

Primary Endpoint

- 1) Compare opioid requirements (in morphine equivalents) between trauma patients with rib and/or sternal fractures receiving liposomal bupivacaine versus standard of care.

Secondary Endpoints

- 1) Compare clinical outcomes and treatment failures including:
 - a. Development of pneumonia, defined as >100,000 cfu/mL bacteria on bronchoalvelolar lavage, or clinically with leukocytosis, pulmonary infiltrate and fever
 - b. Median patient analgesic score by verbal NRS

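### Table 9.4, the only severity scale, comes from healthy volunteers: it can misgrade new minor events in opioid-treated inpatients, and its vital-sign grades do not line up with the Section 9 event limits

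*Combined protocol and SAP*

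**What the plan says.** **Withdrawal.** Section 6 (Intervention) deals with an adverse event during the block: if "the reaction is severe or life-threatening, then the patient will be withdrawn from the study". Section 9 (Level of Risk) repeats the rule and then moves straight to vital signs. It lists physiologic changes that count as an adverse event: for heart rate, a relative change above 40% that lasts more than five minutes, and the absolute criterion "absolute heart rate greater than 160 or less than 50". Limits for systolic pressure, respiratory rate and oxygen saturation come next. None of these limits carries a severity grade. Rhythm or ST changes are expressly said to end a subject's participation; nothing comparable is said of the vital-sign limits. Section 14 adds that subjects are withdrawn, as appropriate, for any adverse event described in Section 9, and does not restrict this to the procedure.

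**Severity.** The investigator is to assess the severity of each event. The only scale given is Table 9.4, whose source note names the "Toxicity Grading Scale for Healthy Adult and Adolescent Volunteers Enrolled in Preventive Vaccine Trials". Grade 3 is headed severe and Grade 4 potentially life-threatening. Grade 3 for local pain reads "Any use of narcotic pain reliever or prevents daily activity".

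**Use of the data.** Section 11 keeps a withdrawn patient's data up to withdrawal. Its sample-size paragraph plans on a 96-hour opioid total of 250 mg against 200 mg oral morphine equivalents.

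**Stopping.** Section 10 has two criteria. The first counts drug-related events whatever their severity. The second is "Serious/life-threatening adverse events, regardless of causality, occur in > 2% of enrolled patients".

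**The concern.** A severity scale has to separate mild from severe events in the patients to whom it is applied. Narcotic use and hospital admission can do that for healthy outpatients. They cannot for trauma patients with an expected stay of at least 72 hours, on a regimen that includes opioids and with opioid consumption as the primary endpoint. The vital-sign rows raise a second problem: values that Table 9.4 calls severe lie inside the limits Section 9 uses to flag a physiologic event, and no sentence connects the two lists.

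The word severe triggers withdrawal. If two investigators can grade the same reaction differently, withdrawal depends on which part of the protocol each has in mind. Safety tables by grade would be affected too. Because withdrawn patients contribute data only up to withdrawal, the 96-hour opioid total is also exposed.

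**Working it through.** The documents state no figure to reproduce on this point. The check sets the passages side by side.

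**1. Vital signs.** Section 9 absolute limits against Table 9.4 (for heart rate, the rows "Tachycardia - beats per minute" and bradycardia):

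| Measure | Section 9 event | Table 9.4 Grade 3 | Mismatch |
|---|---|---|---|
| Heart rate, high | >160 | >130 | 131–160 is Grade 3 but inside the limit |
| Heart rate, low | <50 | <45 | 45–49 is an event, graded 2 (not in itself a conflict) |
| Systolic, high | >180 | >155 | 156–180 is Grade 3 but inside the limit |
| Systolic, low | <80 | <80 | none |
| Respiratory rate, high | >30 | >25 | 26–30 is Grade 3 but inside the limit |
| Respiratory rate, low | <6 | no row | event with no grade |
| Oxygen saturation | fall of 10% or <85% | no row | event with no grade |

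**2. Does the change-from-baseline criterion close the gap?** Only for some patients. At the top of each range:
- Heart rate 160 is a rise of more than 40% only from a baseline below 160/1.4 = 114.3.
- Systolic pressure 180 is a 40% rise only from 180/1.4 = 128.6 or lower.
- Respiratory rate 30 is a 50% rise only from 30/1.5 = 20 or lower.

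A patient who starts above these values can cross the whole range without meeting a Section 9 physiologic criterion.

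**3. Descriptors.** Table 9.4 has 4 local, 7 vital-sign and 5 systemic rows, 16 in all.
- Any narcotic use is sufficient for Grade 3 in 2 rows: local pain and headache.
- An emergency visit or hospitalisation, with no condition named, is Grade 4 in 6 rows: pain, tenderness, diarrhoea, headache, fatigue and myalgia.
- In 6 further rows Grade 4 is a visit or admission for a named condition: tachycardia, bradycardia, systolic and diastolic hypertension, hypotension, and nausea/vomiting. These can still discriminate.
- The other 4 rows (erythema, induration, fever, respiratory rate) use other criteria.

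**4. A literal example.** Section 9 expects temporary pain or discomfort from repeated injections. Such pain is new, so it is reportable. The patient is already in hospital and probably taking opioids: the planning means are 250 mg and 200 mg over 96 hours. Read as written, mild injection-site pain meets the Grade 3 narcotic descriptor and, on the most literal reading, the Grade 4 descriptor. The wording does not separate opioids taken for that pain from opioids taken for fractures in the same chest wall.

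**5. Effect on the endpoint.** A patient withdrawn during the block contributes almost none of the 96-hour total. Suppose, as an assumption, that a fraction w of an arm is lost this way and the truncated totals are analysed as they stand; Section 11 does not say how they are handled.
- Active arm only: its mean falls by 200w, which is 2 mg at w = 1%, 10 mg at 5% and 20 mg at 10%, against a planned difference of 50 mg.
- Both arms equally: the difference becomes 50(1 − w), or 47.5 mg at 5%.

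The values of w only show the scale of the effect. The documents give no basis for choosing one.

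**6. Stopping criteria.** Neither refers to Table 9.4 grades. The first ignores severity. For the second, Section 9 defines serious by outcome and life-threatening as immediate risk of death. What remains is a near-collision of terms with the Grade 4 column label.

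**The case against.** A reader might infer three stronger things, and the documents support none of them.

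- **That there are two rival scales for a severe event.** Section 9's limits say when a physiologic change counts as an event, and only Table 9.4 grades severity. The list of limits is also inclusive and sits beside a broad definition of adverse event, so a heart rate of 140 can still be recorded as one.
- **That Grade 4 is met simply by being an inpatient.** An event must exist before it is graded, and conditions present before enrolment are not reported unless they worsen. Admission and fracture pain are therefore not events in themselves.
- **That stopping-rule counts cannot be interpreted.** The second criterion uses separately defined terms, and the definition of life-threatening excludes events that might have caused death only in a more severe form. A probability of crossing the 2% limit would not measure this defect.

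It can also be said that the narcotic descriptor sits under local reactions and is meant for pain from the injection, and that severity-based withdrawal covers only reactions during the block.

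All of this narrows the point without removing it. The exemption for pre-existing conditions does not reach new injection-site pain or new headache, which are the rows with the narcotic descriptor. The restriction to the block is loosened by Section 14. No sentence says that Table 9.4 defines severe for withdrawal, but the protocol offers no other definition.

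**Conclusion.** The point holds in this limited form and should be corrected. As written, Table 9.4 can assign wrong grades to new minor events in opioid-treated inpatients: 2 rows through narcotic use and 6 of 16 through unqualified hospitalisation. Its severe range does not line up with the Section 9 limits for heart rate, systolic pressure or respiratory rate on the high side, and it has no row for low respiratory rate or oxygen saturation.

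The consequences are inconsistent severity reporting and inconsistent withdrawal, with possible truncation of the primary endpoint. The effect on the endpoint is likely to matter most if withdrawals differ between arms. Its size is unknown.

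This rests on two assumptions: that investigators apply the descriptors literally, and that Table 9.4 is what they use to decide whether a reaction is severe.

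**What to change.** - Reconcile the Section 9 vital-sign limits with Table 9.4, and cover the Section 9 limits that have no grade. The sponsor sets all clinical thresholds; none is proposed here.
- State which definition governs withdrawal, whether reaching a vital-sign limit leads to withdrawal, and how Sections 6, 9 and 14 fit together.
- Replace the narcotic-use and unqualified hospitalisation descriptors with ones that can distinguish between inpatients already on opioids, graded against the pre-injection baseline.
- State in Section 10 that the second stopping criterion uses the Section 9 definitions of serious and life-threatening, and not the Grade 4 label.

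The cost is wording in the protocol and case report form. The drawback is that grades are no longer directly comparable with the published volunteer scale.

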emergency medicine and surgery practitioners are familiar with intercostal blocks for placement of tube thoracostomy. Intercostal blocks do not require additional training, as would be done in the setting of a pain medicine fellowship, and do not incur the risks of hypotension associated with epidural catheters. Additionally, intercostal and paravertebral blocks carry similar risks of pneumothorax or intercostal neurovascular bundle injury.

Study design:

This is an investigator-initiated, single-center, prospective, double-blinded, placebo-controlled trial funded by the United States Air Force. Multi-system, adult trauma patients greater than or equal to 18 years of age admitted to the University of Cincinnati Medical Center (UCMC), an urban American College of Surgeons-verified Level 1 trauma center with more than 3500 annual trauma admissions annually will be identified by the research team. Patients will be screened and those who meet all inclusion/exclusion criteria will be approached for informed consent by study personnel in their rooms. Informed consent will be obtained prior to enrollment and any study procedures are done. Patients will then receive either receive 1 mL of liposomal bupivacaine just below each affected rib or 0.9% sodium chloride peri-intercostal subcutaneous injection (as placebo control) via a 25-G needle. Goal enrollment is 200 patients with 100 patients in each group. Patients included in the study will be followed during inpatient hospitalization through discharge.

6. Research data collection/study procedures:

Intervention

Patients will be identified on admission and will be screened by inclusion/exclusion criteria. After informed consent is obtained they will be randomized into one of two possible groups:

- a. Liposomal bupivacaine intercostal (group 1; interventional)
- b. 0.9% sodium chloride peri-intercostal subcutaneous (group 2; placebo-control)

Patients will be placed on continuous monitoring of heart rate, EKG, and pulse oximetry. Blood pressure and respiratory rate will be measured every 5 to 10 minutes during the procedure and every at least 15 minutes for the first hour after the procedure. All patients undergoing injection will remain on heart rate, EKG, and pulse oximetry monitoring by telemetry for 96 hours following injection.

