A chest xray will be obtained as clinically indicated following the procedure if there is concern for the development of pneumothorax.

Self-reported pain will be measured using the verbal NRS, a 0-10 ordinal scale (e.g., 0 = "no pain"; 10 = "worst pain imaginable").²⁷ Breakthrough opioid dosing

will be guided by a formal inpatient analgesia protocol. Pain assessments will occur every 6 hours or per standard of care for the appropriate setting (e.g., intensive care unit, trauma ward) for the first 96 hours. All opioid dosing will be converted to oral morphine equivalents for comparison purposes. Time to first breakthrough opioid dose will be recorded. Incentive spirometry will be used and assessed and recorded by respiratory therapist, with adjunct inspiratory assistance (e.g., EzPAP) applied per our institutional volume expansion protocol.

Follow-up will occur daily by study coordinators and trauma service physicians for the first 96 hours after block procedure, then daily by the trauma service physicians for 14 days or until discharge from the hospital if it occurs earlier.

Standard of care analgesia regimen on the trauma service will be provided to all patients enrolled in the study, regardless of liposomal bupivacaine or placebo injection. This regimen will be per the Trauma acute multimodality pain management protocol (Appendix).

Typical escalation of analgesics provided for these patients, as deemed medically appropriate based on age and comorbid medical conditions, includes (in order of addition to regimen):

- Acetaminophen, oral or enteral
- NSAIDs, ibuprofen or ketorolac
- Lidocaine 5% transdermal patch
- Oral or enteral tramadol
- Oral or enteral hydrocodone or oxycodone
- IV morphine or hydromorphone, intermittent dosing
- Patient controlled analgesia morphine or hydromorphone
- Long-acting narcotics, including methadone, oxycodone ER, or morphine ER
- Neuromodulating adjuncts, including gabapentin or pregabalin
- Epidural analgesia catheter placement

During this time all adverse events will be recorded. Subjects who experience serious adverse events will be followed until the event resolves. If necessary these patients will be followed up by weekly phone calls as well as at the standard of care clinic visit two weeks post-discharge.

Randomization

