Consequences of poorly controlled pain associated with rib and/or sternal fractures as well as opioid use have been previously outlined above. Risks of liposomal bupivacaine include major and minor adverse events (Tables 1 and 2). Risks will be mitigated by appropriate exclusion of patients with low and high body weights as well as known cardiac history as previously described to minimize pharmacodynamic failure or excess.

Table 9.1. Adverse events occurring in >2% of patients in any treatment group^{15,17,31}

Adverse Event	Bunionectomy ^{17, 20}		Hemorrhoidectomy ^{18, 20}	
	Liposomal Bupivacaine 106 mg (n=97)	Placebo (n=96)	Liposomal Bupivacaine 266 mg (n=95)	Placebo (n=94)
Any treatment-emergent adverse event	58 (59.8)	65 (67.7)	16 (16.8)	17 (18.1)
Gastrointestinal disorders				
Nausea	41 (42.3)	38 (39.6)	8 (8.4)	13 (13.8)
Vomiting	39 (40.2)	36 (37.5)	2 (2.1)	1 (1.1)
Painful defecation	27 (27.8)	17 (17.7)	2 (2.1)	4 (4.3)
Nervous system disorders				
Dizziness	20 (20.6)	30 (31.3)	0 (0.0)	0 (0.0)
Headache	11 (11.3)	25 (26.0)	0 (0.0)	0 (0.0)
Somnolence	5 (5.2)	8 (8.3)	0 (0.0)	0 (0.0)
Skin and subcutaneous tissue disorders				
Skin and subcutaneous tissue disorders	8 (8.2)	7 (7.3)	0 (0.0)	0 (0.0)
Pruritus, generalized	5 (5.2)	6 (6.3)	0 (0.0)	0 (0.0)
Abnormal laboratory investigations	5 (5.2)	3 (3.1)	4 (4.2)	3 (3.2)

Data are no. (%) of patients.

Table 9.2. Incidence of serious adverse events occurring in >1 patient in any treatment group³⁰

	n (%)		
	Liposome Bupivacaine		
	≤266 mg (n = 545)	Bupivacaine HCl (n = 446)	Placebo (n = 190)
Any serious AE	6 (1.1)	24 (5.4)	2 (1.1)
Arthrofibrosis	0	3 (0.7)	0
Cellulitis	0	0	0
Congestive cardiac failure	0	0	0
Atrial fibrillation	0	2 (0.4)	0
Sedation	0	0	0
Hypoglycemia	0	2 (0.4)	0
Deep vein thrombosis	0	2 (0.4)	1 (0.5)

Cardiac and neurotoxicity that are generally seen with increased serum bupivacaine concentrations (i.e. >2000 ng/mL) should serve minimal risk as concentrations seen in previous studies using the maximum FDA-approved dose of 266 mg of liposomal bupivacaine measured maximum concentrations of 867 and <300 ng/mL each.^{15, 28-29} Patients will require and be monitored by a central cardiac monitoring unit to assess for any changes in heart rate or rhythm for the first 96 hours at minimum.

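### Data end at study withdrawal despite an intention-to-treat analysis, so a patient withdrawn for an adverse event contributes a shortened opioid total

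*Combined protocol and SAP*

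**What the plan says.** Section 11 (Data Analysis) names intention-to-treat as the analysis model. The same paragraph then limits a withdrawn patient's contribution to data from before the withdrawal. It gives no method for an incomplete opioid total. The primary endpoint is opioid requirement in morphine equivalents and names no window; for opioid use, 96 hours appears only in the sample-size paragraph.

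The plan has two stated routes to withdrawal for an adverse event, and a third that is unclear:

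- Sections 6 and 9: if a reaction during the block is severe or life-threatening, "then the patient will be withdrawn from the study and no further injections will be administered".
- Section 14: subjects may be withdrawn, where appropriate, for any Section 9 adverse event.
- Section 9 (Level of Risk): "Any non-sinus rhythm or ST segment changes seen on the EKG monitoring strip will lead to immediate subject discontinuation." The sentence gives no period and does not say what is discontinued.

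Follow-up is already planned for the whole window. Section 6 states "All patients undergoing injection will remain on heart rate, EKG, and pulse oximetry monitoring by telemetry for 96 hours following injection" and "Follow-up will occur daily by study coordinators and trauma service physicians for the first 96 hours after block procedure". Section 13 adds a general statement that outcomes are followed through discharge. It does not mention withdrawn patients.

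**The concern.** An intention-to-treat comparison needs the outcome of every randomised patient over the same period. Ending the data at withdrawal breaks this for the patients who had a reaction. For a cumulative outcome the error has a direction: fewer observed hours give a smaller total, so an early withdrawal resembles good pain control.

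If withdrawals are equally common in both arms, the treatment difference shrinks and the variance grows. If they were commoner on liposomal bupivacaine, the shortened totals would favour the drug. The EKG rule matters because it could raise the number of withdrawals, depending on how staff read it.

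**Working it through.** **Inputs.** From Section 11: 250 mg over 96 h on control, 200 mg on active, SD 50 mg. From the study design: 100 per arm. From Table 9.2 (other settings): any serious adverse event in 6/545 on liposomal bupivacaine, 24/446 on plain bupivacaine and 2/190 on placebo; serious atrial fibrillation in 0/545, 2/446 and 0/190. The documents give no expected withdrawal rate, so every rate below is an assumption.

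**1. The plan's own figure.** n per arm = 2(1.96 + 0.842)² × 50²/50² = 15.7, so 16 per arm or 32 in total (34 with the t distribution). This does not reproduce 200. At 100 per arm, power is above 0.999. The mismatch is a separate matter and is not used as support here.

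**2. One withdrawn patient.** With even use, a patient withdrawn at hour t contributes 250 × t/96 mg: 0 mg at 0 h, 62.5 mg at 24 h and 125 mg at 48 h.

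**3. Equal withdrawal in both arms.** Let a share p in each arm have a total of zero (the worst case). An arm with full mean m then has mean (1−p)m and variance (1−p)50² + p(1−p)m².

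| p | Difference, mg | Standardised difference | Power |
|---|---|---|---|
| 2% | 0.98 × 50 = 49.0 | 0.83 | >0.999 |
| 5% | 0.95 × 50 = 47.5 | 0.68 | 0.998 |
| 10% | 0.90 × 50 = 45.0 | 0.54 | 0.97 |

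This comfort depends on SD 50. With an assumed SD of 125 mg, power without truncation is 0.807. It falls to 0.724 at p = 5% and 0.644 at p = 10%.

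**4. Unequal withdrawal, no true effect.** With shares pa (active) and pc (placebo), and a fraction f of the total retained, the false difference is (pa − pc)(1 − f) × 250 mg.

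Table 9.2 gives no reason to expect pa to exceed pc. Any serious event occurred in 6/545 = 1.10% on liposomal bupivacaine and 2/190 = 1.05% on placebo. If all such patients were withdrawn at time 0, the false difference would be (0.01101 − 0.01053) × 250 = 0.12 mg.

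For serious atrial fibrillation the exact two-sided 95% upper limits are 0.67% (0/545), 1.61% (2/446) and 1.92% (0/190). The table below gives results for cut-off at 0, 24 and 48 h (f = 0, 0.25, 0.5). Error rates come from 40,000 simulated trials per cell with normal totals of mean 250 and SD 50. Without truncation both tests give 0.048 to 0.049.

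| Active vs placebo | False difference, mg | t-test error | Rank-sum error |
|---|---|---|---|
| 0.67% vs 0% | 1.7 / 1.3 / 0.8 | 0.054 / 0.054 / 0.053 | 0.051 / 0.051 / 0.050 |
| 1.61% vs 0% | 4.0 / 3.0 / 2.0 | 0.077 / 0.064 / 0.058 | 0.054 / 0.053 / 0.054 |
| 3% vs 1% | 5.0 / 3.8 / 2.5 | 0.081 / 0.073 / 0.064 | 0.054 / 0.056 / 0.057 |
| 5% vs 1% | 10.0 / 7.5 / 5.0 | 0.180 / 0.140 / 0.101 | 0.077 / 0.074 / 0.077 |

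The first two rows are tied to Table 9.2; the last two are assumptions only. With SD 125, t-test error is about 0.05 to 0.06 up to 3% vs 1%, and 0.06 to 0.08 at 5% vs 1%.

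**The case against.** Much of the case on the other side stands.

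- **The EKG rule may concern the block only.** Its paragraph opens with reactions during administration, and the block is given once, so an immediate stop has practical meaning mainly while injections are under way. This is a fair reading, but the sentence does not say so. Telemetry runs for 96 h, and after the block no injections remain to be stopped.
- **Section 11 does not say that a partial sum is treated as a full total.** This is correct, so the bias is conditional. Section 11 offers no other method, however.
- **The scenarios lean one way.** The first two rows pair an upper limit with 0% on placebo, although placebo's own upper limit is the highest of the three. The second row uses the limit for a different drug. In both rows the rank-sum test, which the plan specifies for non-normal data, stays near 0.05. In the other direction, Table 9.2 counts only serious atrial fibrillation and so understates how often any rhythm or ST change would occur.
- **Section 13 promises follow-up through discharge.** This general statement does not override Section 11's specific rule for withdrawn patients.

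A reader might infer that the EKG rule removes every patient with chronic atrial fibrillation on the first strip, since Section 13 does not list that rhythm as an exclusion. The documents do not support so firm a reading. ST changes imply a comparison, Section 9 monitors "to assess for any changes in heart rate or rhythm for the first 96 hours at minimum", and it says "Any medical condition present prior to study enrollment should not be reported as an adverse event" (unless it worsens). Section 9 also refers to excluding patients with a known cardiac history as described earlier, which may or may not reach beyond the listed criteria. A rhythm present before injection should in any case balance across arms under randomisation.

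**Conclusion.** The point holds as a minor one. Ending data at withdrawal conflicts with the stated intention-to-treat analysis, and it applies at least to the severe reactions that Sections 6 and 9 expressly withdraw. Whether the EKG rule adds to these depends on an undefined word.

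The likely effect on the result is small. Equal losses of up to 10% per arm leave power at 0.97 or more under the plan's SD of 50 mg, though the loss of power would be larger if the SD were nearer 125 mg. These figures assume even opioid use over 96 h and partial totals analysed as they stand.

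A reader might go further and infer that the result will be biased in favour of the drug. That needs more withdrawals on the active arm, which the documents do not show. Section 9 says cardiac and neurotoxicity "should serve minimal risk as concentrations seen in previous studies using the maximum FDA-approved dose of 266 mg of liposomal bupivacaine", and Table 9.2 ("Incidence of serious adverse events occurring in >1 patient in any treatment group") has no serious atrial fibrillation on liposomal bupivacaine and nearly the same overall rate of serious events as placebo.

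**What to change.** In Section 11, replace the rule on withdrawn patients with this: for every patient stopped or withdrawn for an adverse event, opioid use and other outcomes are collected to 96 h or discharge, unless the patient withdraws consent for data collection, and are analysed in the arm to which the patient was randomised.

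As a secondary clarification, state in Section 9 that discontinuation for an EKG finding means no further injections, and state the period the rule covers (the block procedure or the full 96 h). Whether to limit the rule to rhythm changes that are new compared with a pre-injection strip, or instead to exclude non-sinus rhythm at entry, is a clinical decision for the investigators.

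The cost is slightly more data collection on a few patients who are already followed daily. If the investigators choose the comparison with baseline, a pre-injection strip must also be kept. Stopping injections after a reaction is unaffected.
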